9.1.4 Final analysis for the primary endpoint

If the study continues, after all 23 subjects are evaluable for efficacy and safety the study data set will be locked. Out of the total of 23 subjects, if the number of subjects with PFS6 is 16 or more, the conclusion will be that the trial has demonstrated a statistically significant improvement above a 50% PFS6 rate. The final estimated PFS6 rate will also be presented, along with a lower 90% confidence interval.

9.1.5 Definition of study population for analysis

All subjects who undergo at least one dose of the study treatment will be included in the analysis population. If applicable, "Intention-to-treat" analyses will be performed for an endpoint. If the endpoints for a subject cannot be assessed (for example, a subject drops early prior to the 6 months assessments due to toxicity), it will be considered to be an event that does not favor the study therapy (e.g., disease progression for the primary outcome).

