1.2 Secondary Objectives

- 1.2.1 To determine the overall response rate to poly-ICLC in the treatment of children with recurrent low grade gliomas; tumor assessments are to be performed per 3D measurements.
- 1.2.2 Progression free survival over the course of the study.
- 1.2.3 Overall survival at 6 months – the time from starting study therapy to death from any cause.
- 1.2.4 To assess the toxicity associated with treatment with poly-ICLC in pediatric patients with recurrent low grade gliomas.
- 1.2.5 To study the effect of treatment with poly-ICLC on the signaling pathways controlling apoptosis in low grade glioma tumor cells.
- 1.2.6 To determine if surrogate markers of tumor response and progression can be identified in the serum, PBMC and/or cerebrospinal fluid of patients with recurrent low grade gliomas treated with poly-ICLC. Proteomics analysis will be performed to obtain protein levels of these markers such as OAS, interferon α , β , γ , PKR kinase, phosphorylation state of eIF2a, and induction of p21^{waf-1}.

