8.0 CRITERIA FOR REMOVAL FROM PROTOCOL THERAPY AND OFF STUDY CRITERIA

8.1 Criteria for Removal from Protocol Therapy

a. Progressive disease

Note: Transient enlargement of enhancing disease with subsequent shrinkage has been reported during poly-ICLC treatment. Because of this, if the patient has progressive disease by the conventional definition above but does not have unacceptable progression by the definitions below, the treating physician and patient have the options of continuing poly-ICLC treatment on this protocol or of discontinuing treatment.

b. Criteria for unacceptable progression: See definitions of tumor progression outlined in section 7.1.3

1. >50% increase in the product of the three perpendicular diameters of initial tumor relative to the initial baseline measurement – LxWxT (current can) $> 1.5 \times$ LxWxT (initial scan), or the development of any new sites of disease independent of the response of the initial tumor. Post radiation changes are often seen on post-treatment imaging studies, so that classification of a patient as having progressive disease may require several serial MRI's if the child has received radiation within the preceding 12 months.

2. Unacceptable worsening of neurological symptoms that cannot be controlled with corticosteroids.

3. Any other radiological or clinical evidence of worsening to the extent that the treating physician feels it is not in the patient's best interest to continue poly-ICLC.

c. Physician determines it is in patient's best interest.

- d. Patient and/or parent/guardian refusal to continue or inability to comply with protocol
- e. Grade 3 or 4 toxicity that does not resolve to Grade 1 within three weeks after interruption of therapy, or recurrent grade 3 or 4 toxicity at a reduced dose level (see section 4.2).

Note: If final analysis confirms a beneficial effect of poly-ICLC, and/or if tumor recurs after withdrawal from poly-ICLC at the end of the 2-year prescribed treatment period, participating subjects may be offered continued treatment with poly-ICLC (subject to drug availability at that time).

- f. Completion of planned therapy.

Subjects who are off protocol therapy are to be followed until they meet the criteria for Off Study (see below). Follow-up data will be required, unless consent is withdrawn, every 3 months for the first year, every 4 months for the second year, every 6 months for the third year, and then yearly thereafter

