8.2 Off Study Criteria

- a. Death.
- b. Lost to follow-up.
- c. Entry into another therapeutic study.
- d. Withdrawal of consent for any further data submission.

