9.0 STATISTICAL CONSIDERATIONS

a. The primary goal of this trial is to obtain preliminary estimates of the ability of poly-ICLC to prevent or delay disease progression in subjects with recurrent or newly diagnosed low-grade gliomas. The primary endpoint will be progression free survival rate at 6 months (PFS6) after starting therapy. Progression free survival is defined as the time from starting study therapy to tumor progression, tumor recurrence, death from any cause, or occurrence of a second malignant neoplasm. Tumor assessment for the primary endpoint will be based on modified McDonald's criteria (section 7.1.2). Tumor assessment results obtained based on the 3D measurements will be considered secondary. The overall response rate (ORR) at 6 months will be a secondary endpoint. The ORR will include complete response, partial response, and stable disease (see Section 7.1.4). Time to progression will be documented for all patients who progress.

b. The second goal is to further define the side effects and toxicity of this regimen in these subjects. Secondary endpoints also include tumor ORR at 2 years after starting therapy and also the duration of the good response. Tumor response will be assessed at 3, 6, 9, 12, 18, 24 months after starting the therapy, as well as at the time of going off study if prematurely. Other secondary endpoints also include tumor response rates based on 3 dimension measurements as in section 7.1.3 at 3, 6, 9, 12, 18, 24 months after starting the therapy, progression free survival and overall survival over the course of the study.

c. The third goal will be to examine a series of biochemical determinations (e.g. serum OAS and interferon levels, PKR, phosphorylation state of eIF2a, p21^{waf-1}) as surrogate markers for sensitivity of patients to poly-ICLC. These will be compared to clinical response data. A subset of the proteins involved in apoptosis and signaling pathways will be looked into specifically to assess the effect of the study treatment on these signaling pathway changes. The specific endpoints are:

- Association of baseline levels of proteins (such as OAS, interferon, PKR, phosphorylation state of eIF2a, p21^{waf-1}) in serum, PBMC and/or cerebrospinal fluid with tumor response status at 6 months after treatment with Poly-ICLC.

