9.1.6 Accrual and study duration

All the 23 patients are expected to be accrued in 3 years and the total study duration will be about 5 to 5.5 years.

9.2: Analysis of Results

9.2.1: Analysis of anti-tumor activity

The "best response" rate is defined as the percent of evaluable subjects who experience a CR or PR or SD (see Section 7.1.2). The best response rates as well as overall response rates at 6 and 24 months will be estimated and exact lower one sided confidence intervals for the true response rates will be presented (Jung, 2004). The duration of response for each subject that has tumor response will be summarized in a table. The same analysis will be done for the tumor response rate based on 3 dimension measurements as in section 7.1.3.

9.2.2: Summary of toxicities and side effects

All observed toxicities and side effects will be recorded on toxicity sheets and the data collection forms. Toxicity information including type, severity, time of onset and resolution, and probable association with the study drugs will be recorded. Toxicities will also be analyzed by NF1 status (NF1 vs. non NF1 subject cohorts). Tables will be constructed to summarize the observed incidence by type of toxicity and severity.

9.2.3: Analysis of Survival

Overall survival and progression-free survival rates will be estimated using the Kaplan-Meier method (Kaplan, 1958).

9.2.4: Analysis of biochemical measures.

Laboratory studies will be done on subject's serum and peripheral blood drawn prior to and at two weeks after starting treatment with Poly ICLC. Levels and changes in the measurement of serum markers and proteins such as OAS, interferon α , β , γ , PKR kinase, eIF2a, and p21^{Waf-1} will be determined via proteomic analysis. For each marker, a Fisher's exact test or a Wilcoxon rank sum test will be used to assess the association of a baseline protein level or changes from baseline against tumor response status at 6 months. A log rank test will be used if the outcome is progression free survival.

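### Required follow-up ends when a child enters another treatment trial (8.2c), so later deaths need not be collected and Kaplan-Meier overall survival may be overstated

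*Combined protocol and SAP*

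**What the plan says.** **Endpoint.** Section 1.2.3 lists OS at 6 months, defined as "the time from starting study therapy to death from any cause". Section 9.0b goes further and names "progression free survival and overall survival over the course of the study" as secondary endpoints. Section 9.1.6 expects accrual over 3 years and a total duration of about 5 to 5.5 years.

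**Method.** The whole of 9.2.3 is one sentence: "Overall survival and progression-free survival rates will be estimated using the Kaplan-Meier method". It gives no censoring event or date.

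**Follow-up.** Section 8.1 says: "Subjects who are off protocol therapy are to be followed until they meet the criteria for Off Study". The schedule is "every 3 months for the first year, every 4 months for the second year, every 6 months for the third year", then yearly, unless consent is withdrawn. Section 8.2 has four off-study criteria: (a) death, (b) loss to follow-up, (c) "Entry into another therapeutic study", and (d) withdrawal of consent to further data submission.

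**Unassessable endpoints.** For a subject whose endpoints cannot be assessed, 9.1.5 says that "it will be considered to be an event that does not favor the study therapy (e.g., disease progression for the primary outcome". It does not say whether this reaches the Kaplan-Meier endpoints.

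**The concern.** OS across the study needs each child's survival status up to death or the end of the study. Criterion 8.2c differs from the other three. The child is alive, has not been lost and has not withdrawn consent, but the plan no longer requires anyone to ask about survival.

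Kaplan-Meier estimation assumes that a censored child has the same later risk of death as the children still followed. Progression is a ground for leaving protocol therapy (8.1a), and a child who has progressed is a plausible candidate for another trial. If such children are the main entrants, those at highest risk leave the risk set and their deaths go uncounted. No analysis can recover deaths that were not collected.

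What is at stake is the later part of the OS curve. A child who has already progressed has had a PFS event, since PFS counts "tumor progression, tumor recurrence, death from any cause, or occurrence of a second malignant neoplasm". For that child 8.2c affects OS only.

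**Working it through.** **Inputs from the documents.** n = 23 if the trial completes and n = 14 if it stops at Stage 1 (9.1.1, 9.1.4). Accrual takes 3 years and the study lasts 5 to 5.5 years (9.1.6). The numbers of deaths and of trial entrants are not given, so they appear below as assumed values.

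**1. The plan's own figures.** The plan states none for OS. Its quantified design is binary PFS6: stop at 7 or fewer of 14, succeed at 16 or more of 23. Exact binomial calculation gives an early-stopping probability of 0.605 at a 50% rate (stated 61%), type I error 0.046 (limit 5%) and power 0.802 at 75% (stated 80%). This test does not depend on later follow-up, because a subject who cannot be assessed at 6 months counts as a failure.

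**2. One unrecorded death, no other censoring.** One child enters another trial, is censored, and dies before time t. Let d be the other recorded deaths by t, of which a come before the censoring.

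- Kaplan-Meier OS = (23 − a)/23 × (22 − d)/(22 − a)
- True OS = (22 − d)/23
- Overstatement = (22 − d) / [23 × (22 − a)]

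The largest value is at a = d: 1/23 = 4.35 points. The smallest is at a = 0: (22 − d)/506, which is 4.35 points at d = 0, 20/506 = 3.95 at d = 2 and 17/506 = 3.36 at d = 5. For n = 14 the largest is 1/14 = 7.14 points and the smallest is (13 − d)/182, for example 8/182 = 4.40 at d = 5.

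**3. The entrant who survives.** With a = 0, Kaplan-Meier OS is (22 − d)/22 and true OS is (23 − d)/23, so OS is understated by d/506 (5/506 = 1.0 point at d = 5). If the entrant dies by t with probability π, the expected shift is π/23 − d/506, which is positive only when π > d/22. So the estimate leans upward only if entrants die more often than the other 22 children.

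**4. With administrative censoring.** The last children accrued have about 5 − 3 = 2 to 5.5 − 3 = 2.5 years of follow-up, so beyond that time the risk set shrinks and 4.35 points is no longer a ceiling. Suppose 12 of 23 were censored alive before the child's death and no other death occurred. Then 23 − 12 = 11 are at risk. Kaplan-Meier OS is 10/11 = 0.909 if the death is recorded and 1.000 if it is not, a gap of 1/11 = 9.1 points.

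**5. When it acts (illustration on assumed rates).** A large simulation (400,000 subjects, exponential times) assumed PFS6 of 50% or 75%, one-year survival after progression of 60% to 90%, and 25% to 75% of progressors entering another trial one month after progression. Censoring at entry overstated OS by about 0.1 to 3 points at 6 months and about 1 to 15 points at 24 months. With PFS6 75%, post-progression survival 80% and half entering, 24-month OS was 0.890 against a true 0.845. These results show the timing and direction under the assumptions; they do not predict this trial's error.

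**The case against.** **Nothing in the documents shows that trial entry is informative.** They give no entry rate and no death rate after progression. Section 8.1 lets a child with conventional but not unacceptable progression stay on treatment, so progression need not lead to 8.2c. The background says that children with low-grade astrocytomas often survive many years, though not specifically after recurrence. This stands: the supportable wording is that OS may be overstated.

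**The listed objective is OS at 6 months, where the effect is small.** That also stands, but 9.0b adds OS across the study, and there the gap matters more.

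**A death may still be learned of.** Section 5.3 asks for a death report form if a patient dies. It does so among the evaluations at end of therapy or relapse, and it requires no contact after a child is off study. Some deaths may therefore become known, but collecting them is not required.

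**A stronger reading of 9.1.5 is tempting.** A reader might infer that the plan codes a living child who drops out as an OS death, or adds a PFS event outside the definition. The documents do not support that. Both examples in 9.1.5 concern the 6-month primary outcome, intention-to-treat analysis is qualified as applying only where applicable, OS is defined by death, and 9.2.3 names Kaplan-Meier. An analyst would censor a child last known alive. What remains is a missing sentence on scope and censoring dates.

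**Conclusion.** The point holds as a gap in required follow-up. Followed as written, 8.1 with 8.2c ends the collection of survival status at entry into another treatment trial, while 9.0b reports OS across a study of about 5 to 5.5 years.

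With no other censoring, one unrecorded death shifts later OS by up to 4.3 points (n = 23) or 7.1 points (n = 14). With administrative censoring the shift can be larger, 9.1 points in the example. No total can be stated, because the number of such children is unknown. The upward direction rests on the assumption that entrants have a higher risk of death than those still followed.

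A reader might infer that the trial's conclusion is at risk. It is not. The PFS6 decision is unaffected, and OS here is a single-arm secondary estimate with no decision threshold. The change is worth making because it is cheap and must be made before the deaths occur.

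**What to change.** **Main change, in 8.2c.** State that survival-status follow-up continues after entry into another therapeutic study, at the existing 8.1 intervals, unless consent is withdrawn. Subjects lost (8.2b) or withdrawn from data submission (8.2d) stay censored; this change does not recover them.

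**Minor clarification.** In 9.1.5, say that the failure rule applies to binary PFS6. In 9.2.3, say that Kaplan-Meier OS is censored at the date last known alive and PFS at the last disease assessment.

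**Cost.** One sentence in 8.2 and two or three in 9.1.5 and 9.2.3. The added work is survival-status contact for trial entrants only: 12/3 + 12/4 + 12/6 = 4 + 3 + 2 = 9 contacts in the first three years off therapy, then one a year, so at most 11 per affected child over five years. Sample size and the PFS6 decision rule do not change.

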9.1.6 Accrual and study duration

All the 23 patients are expected to be accrued in 3 years and the total study duration will be about 5 to 5.5 years.

9.2: Analysis of Results

9.2.1: Analysis of anti-tumor activity

The "best response" rate is defined as the percent of evaluable subjects who experience a CR or PR or SD (see Section 7.1.2). The best response rates as well as overall response rates at 6 and 24 months will be estimated and exact lower one sided confidence intervals for the true response rates will be presented (Jung, 2004). The duration of response for each subject that has tumor response will be summarized in a table. The same analysis will be done for the tumor response rate based on 3 dimension measurements as in section 7.1.3.

9.2.2: Summary of toxicities and side effects

All observed toxicities and side effects will be recorded on toxicity sheets and the data collection forms. Toxicity information including type, severity, time of onset and resolution, and probable association with the study drugs will be recorded. Toxicities will also be analyzed by NF1 status (NF1 vs. non NF1 subject cohorts). Tables will be constructed to summarize the observed incidence by type of toxicity and severity.

9.2.3: Analysis of Survival

Overall survival and progression-free survival rates will be estimated using the Kaplan-Meier method (Kaplan, 1958).

9.2.4: Analysis of biochemical measures.

Laboratory studies will be done on subject's serum and peripheral blood drawn prior to and at two weeks after starting treatment with Poly ICLC. Levels and changes in the measurement of serum markers and proteins such as OAS, interferon α , β , γ , PKR kinase, eIF2a, and p21^{Waf-1} will be determined via proteomic analysis. For each marker, a Fisher's exact test or a Wilcoxon rank sum test will be used to assess the association of a baseline protein level or changes from baseline against tumor response status at 6 months. A log rank test will be used if the outcome is progression free survival.

All the p-values will be adjusted using the Benjamini & Hochberg method to control the false discovery rate (FDR) due to the fact that there may be thousands of proteins produced by proteomics. A marker will be claimed significant at $FDR \leq 0.05$. To assess the effect of the study treatment on signaling pathways such as the one controlling apoptosis, paired t-tests will be used to compare if there are significant changes from baseline for the proteins involved in these pathways. To assess differential effects on these pathways between the subjects who had a response and those who did not, gene set enrichment analysis (GSEA) can be performed to see if a pathway is significantly up- or down-regulated in the patients with a response. These analyses will help to understand how poly-ICLC limits tumor growth and ultimately to identify patients who will benefit most from this form of therapy if it is effective.

10.0: ADVERSE REACTION REPORTING AND TOXICITY CRITERIA

The timely reporting of adverse drug reactions (including toxic deaths) is required by the Food and Drug Administration. Reactions definitely felt not to be treatment related should not be reported. However, a report should be submitted if there is any suspicion of drug effect or in the case of Serious Adverse Events. The reporting of adverse reactions is in addition to and does not supplant the reporting of toxicities as part of the data reporting for this study.

Serious Adverse Events (SAEs) Timely reporting of all serious adverse events or drug reactions (including toxic deaths) is required by the Food and Drug Administration, regardless of attribution. The reporting of serious adverse reactions is in addition to and does not supplant the reporting of toxicities as part of the data reporting for this study.

Adverse event is defined as any unfavorable and unintended sign (including an abnormal laboratory finding), symptom or disease temporally associated with the use of a medical treatment or procedure regardless of whether it is considered related to the medical treatment or procedure (attribution of unrelated, unlikely, possible, probable or definite).

A Serious Adverse event is any adverse event, occurring at any dose that is fatal or life-threatening, results in persistent or significant disability/incapacity, requires in-patient hospitalization or prolongation of existing hospitalization is a congenital anomaly/birth defect, or is an important medical event.

Relationship/attribution: The Investigator will be asked to document his/her opinion of the relationship of the event to study medication as follows:

- 1) *Unrelated*: The adverse event is clearly not related to the investigational agent(s).
- 2) *Unlikely*: The adverse event is doubtfully related to the investigational agent(s).

- 3) *Possible*: The adverse event may be related to the investigational agent(s).
- 4) *Probable*: The adverse event is most likely related to the investigational agent(s).
- 5) *Definite*: The adverse event is clearly related to the investigational agent(s).

10.1: Reporting Adverse Drug Reactions Occurring with Investigational Agents

Within 24 hours of recognition, contact the Principal Investigator or his designee by telephone to verify the identification process and the existence of an adverse drug reaction or toxic death.

The following data **must** be reported to the study PI:

- Subject identification number
- Presenting diagnosis, Description of event
- Laboratory data supporting event
- Total and daily doses of suspected drug
- Time of event
- Type and grade of adverse event
- Methods used to recognize and characterize the effect
- Physician attribution/relationship of event to study drug (see above)

The participating site must then submit a completed adverse event case report form to the coordinating site.

Within 10 days of the adverse event, a completed NCI Adverse Reaction Form for Investigational Agents with the NCI protocol number should be submitted to the IRB for life threatening (Grade 4) and fatal known reactions (except Grade 4 myelosuppression) or any unexpected, unanticipated Grade 2 and 3 reactions that are possibly, probably, or definitely attributed to the study drug.

A completed (NCI) Adverse Reaction Form for Investigational Agents should be sent electronically or by FAX to the FDA (see Appendix IV for the electronic links). Oncovir will be notified as soon as an adverse event form has been submitted.

10.2: Toxicity Criteria.

The NCI Common Terminology Criteria for Adverse Events (CTCAE) version 4.0 will be used and referenced. The site, measure, grade, relationship, action taken, and outcome for all toxicities (grades 3 and 4 as well as any unexpected, unanticipated Grade 2 reactions that are possibly, probably, or definitely attributed to the study drug) are to be reported on the appropriate toxicity monitoring and adverse event forms.

10.3: Data Safety Monitoring

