7.1.4 Response Assessment

Tumor response will be assessed at 3, 6, 9, 12, 18, 24 months after starting the therapy, as well as at the time of going off study if prematurely. The overall response rate (ORR), defined as the percent of evaluable subjects who experience a complete response or partial response or stable disease, will be determined. The primary endpoint will be progression free survival rate (per MacDonald Criteria) at 6 months after starting therapy. Secondary endpoints also include tumor ORR at 6 months and 2 years after starting therapy and also the duration of the 'good' response. The traditional overall response rate (CR's and PR's only) will also be summarized.

Each subject will be classified according to their "best response" for the purposes of analysis of treatment effect. Best response is determined from the sequence of the objective statuses described above.

Any subject removed from study protocol because of unacceptable progression (see Section 8.1) will be counted as progressive disease in the efficacy analysis.

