- Association of baseline levels of proteins (such as OAS, interferon, PKR, phosphorylation state of eIF2a, p21^{waf-1}) in serum, PBMC and/or cerebrospinal fluid with progression free survival.
- Association of changes in levels of proteins (such as OAS, interferon, PKR, phosphorylation state of eIF2a, p21^{waf-1}) serum, PBMC and/or cerebrospinal fluid from baseline with tumor response status at 6 months after treatment with Poly-ICLC.
- Association of changes in levels of proteins (such as OAS, interferon, PKR, phosphorylation state of eIF2a, p21^{waf-1}) in serum, PBMC and/or cerebrospinal fluid from baseline with progression free survival.

9.1: Study Design and Justification of Sample size

9.1.1 This is a single arm study, to determine the radiographic progression free survival (PFS) rate to poly-ICLC in the treatment of children with recurrent or progressive low grade gliomas. The primary endpoint is the progression free survival status at 6 months (PFS6) after starting therapy. The tumor response categories will include complete response, partial response, stable disease or progressive disease, as assessed according to section 7.1.2.

Simon's optimal two-stage design will be used for this study (Simon, 1989). Suppose 50% is the uninteresting level, i.e., if the PFS6 rate is $\leq 50\%$, we will consider the new regimen as not promising. This 50% baseline response rate in the absence of treatment is from historical experience (this rate was also used by the Everolimus study which is a phase II study for recurrent or progressive LLG in children), also taking into account that this study patient population are more refractory. We will test the null hypothesis $H_0: p \leq 50\%$ against the alternative hypothesis $H_1: p > 75\%$, where p is the PFS6 rate. The two stage design proposed below will have 80% power to reject the null and conclude that the true response rate is above 50%, if the true response rate is $\geq 75\%$, at 5% significance level.

The study design can be described in detail as follows:

Stage 1: Fourteen subjects will be accrued; accrual will be held up until the PFS6 results for all the 14 subjects are known. The trial will be terminated at Stage 1 if ≤ 7 subjects have a PFS6 response; otherwise it continues to Stage 2. Note that any subject who goes off study early due to toxicity, will be counted as a non-response (an intent to treat analysis).

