Stage 2: Nine more patients will be accrued. We will reject the therapy if among all the 23 (14+9) subjects, the number of patients who have a defined response is ≤ 15 .

Early stopping probability: Under this design, if the null hypothesis is true, the probability of stopping the trial early will be 61%.

9.1.2 Interim analysis and early stopping for efficacy:

The interim analysis will be conducted as soon as the first 14 patients have accrued and are evaluable for the primary outcome. If ≤ 7 subjects had a defined response, the trial will be stopped early for lack of efficacy.

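### Response rates in 7.1.4 and 9.2.1 are percentages of undefined evaluable subjects, which conflicts with the all-treated rule in 9.1.5 and can only raise the reported rates

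*Combined protocol and SAP*

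**What the plan says.** Section 7.1.4 has the overall response rate "defined as the percent of evaluable subjects who experience a complete response or partial response or stable disease". Section 9.2.1 says of best response that the "rate is defined as the percent of evaluable subjects who experience a CR or PR or SD", and it asks for exact one-sided lower confidence limits for best response and for the overall response rates at 6 and 24 months. The same analysis is to be repeated on the three-dimensional measurements.

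Section 9.1.5 sets the analysis population: "All subjects who undergo at least one dose of the study treatment will be included in the analysis population". It adds that when a subject's endpoints cannot be assessed, the result counts against the therapy. Early drop-out for toxicity and progression for the primary outcome are given only as examples, so the rule covers endpoints in general.

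The word evaluable also appears in the primary analysis. The interim takes place "as soon as the first 14 patients have accrued and are evaluable for the primary outcome" (9.1.2), and "after all 23 subjects are evaluable for efficacy and safety the study data set will be locked" (9.1.4). Section 3.1 plans accrual to 24 evaluable subjects, whereas section 9.1 uses 23.

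**The concern.** The two denominators give different answers from the same data, and each can be cited to the protocol. Section 7.1.1 defines measurable, evaluable and non-evaluable disease. Those are descriptions of lesions and do not say which children belong in a response rate.

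The children affected are those with no assessment at the time point. Section 9.1.5 keeps them and counts them as unfavourable; 7.1.4 and 9.2.1, read literally, remove them. The response rates here include stable disease, so a child who stays on study without progressing is a success. Removing children who left early therefore makes the regimen look better. The 24-month rate has the most time for such losses to build up.

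**Working it through.** **1. The plan's own design figures.** Inputs from 9.1.1: null PFS6 rate 0.50, alternative 0.75, stop if 7 or fewer of 14 succeed, reject the therapy if 15 or fewer of 23 succeed.

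- Early stopping under the null: P(Bin(14, 0.5) ≤ 7) = 0.6047, against the stated 61%.
- Probability of declaring success: sum over x = 8 to 14 of P(Bin(14, p) = x) × P(Bin(9, p) ≥ 16 − x). At p = 0.50 this is 0.0462, within the stated 5%. At p = 0.75 it is 0.8016, against the stated 80%.

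The design reproduces with all 14 and all 23 subjects in the denominators.

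**2. Effect on the response rates.** Let N be the number treated, m the number unassessed and not already progressive disease, and k the number with CR, PR or SD.

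- Under 9.1.5 the rate is k/N.
- Under the literal wording of 7.1.4 and 9.2.1 it is k/(N − m).
- The difference is km / [N(N − m)], which is never negative. The second rate cannot be lower than the first.

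N = 23 comes from section 9.1. The documents give no response count or drop-out share, so k = 14 and m = 1 to 3 are assumptions for illustration. The bounds are Clopper-Pearson at an assumed one-sided 95% level and make no allowance for the two-stage design.

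| Children dropped (m) | Rate | Gain over 14/23 | Exact lower 95% bound |
|---|---|---|---|
| 0 | 14/23 = 60.9% | – | 41.7% |
| 1 | 14/22 = 63.6% | 2.8 points | not computed |
| 2 | 14/21 = 66.7% | 5.8 points | 46.4% |
| 3 | 14/20 = 70.0% | 9.1 points | 49.2% |

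**3. Which children are in m.** Several rules already keep early leavers in the count as failures.

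- 7.1.2 includes in progressive disease clear clinical worsening, and failure to return because of death or deterioration unless clearly unrelated to the cancer.
- 7.1.4 counts removal for unacceptable progression as progressive disease.
- 7.1.4 and section 5.0 call for an assessment when a child goes off study early.

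That leaves mainly non-progressing children who go without a scan after toxicity, refusal or loss to follow-up. For best response m is smaller still, because 7.1.4 takes it from the sequence of assessments and any on-study assessment is enough. On the three-dimensional criteria m may be somewhat larger, since 7.1.3 has no clause on failure to return.

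**4. The primary endpoint.** Section 9.1.1 holds accrual until PFS6 is known for all 14 and counts toxicity drop-outs as non-response. The stage 2 rule and 9.1.4 decide on all 23. Section 9.1.5 scores an unassessable primary outcome as progression. No section provides for replacing a treated child.

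**The case against.** The strongest defence is that 9.1.5 already governs. It is the section that defines the analysis population, and the progressive-disease rules in 7.1.2 and 7.1.4 catch most children who leave because they are doing badly. This limits the size of the problem but does not remove the conflict: for the remaining leavers, 9.1.5 is the only rule that keeps them in, and the denominators in 7.1.4 and 9.2.1 contradict it. The phrase in 9.1.5 that intention-to-treat analyses are done where applicable leaves the choice open.

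A second defence is that evaluable has a sensible meaning. Section 3.2.3 (f, g) admits children on vision loss or positive CSF cytology alone, and some may have no measurable or evaluable tumour. This stands as a reason to define the term and to say how such children are handled.

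Two stronger readings are tempting, and the documents do not support either.

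- *A very large effect at 24 months.* With assumed counts, 8 of 12 still scanned is 67%, against 8/23 = 35%. That drops all 11 unscanned children, including those already counted as progressive disease. If 8 of the 11 had progressed (also assumed), the comparison is 8/20 = 40% against 35%.
- *An inflated primary type I error.* If unassessed children were replaced and the all-treated PFS6 rate were 50%, the rate among those counted would be 0.50/(1 − d). The type I error would then be 7.6%, 12.5% or 20.2% for assumed unassessed shares d of 5%, 10% or 15%. The plan states no replacement. Without it, and with the cut-off of 16 kept, leaving unassessed children out gives the same decision as counting them as failures. In 9.1.2 and 9.1.4, evaluable reads naturally as timing.

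**Conclusion.** The point holds for the secondary response rates. Sections 7.1.4 and 9.2.1 use an undefined evaluable denominator that conflicts with 9.1.5, and following it literally can only raise ORR and best response or leave them unchanged. In the illustration, losing 2 or 3 of 23 children moves a 61% rate to 67% or 70%. The direction is certain; the size rests on assumed counts, because the documents give no drop-out share, and it is limited by the existing progressive-disease rules.

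The primary PFS6 test is not shown to be wrong. Its denominators are 14 and 23 with unassessed children as failures, and on that basis its type I error is 4.6%. The 24 evaluable subjects in 3.1 do not match the 23 in section 9.1. That wording leaves some room for a replacement reading, but it does not establish a replacement rule.

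**What to change.** In 7.1.4 and 9.2.1, replace evaluable subjects with all subjects who received at least one dose, referring to 9.1.5. State that a child with no assessment at the time point counts as a non-responder; for best response, this applies to a child with no on-study assessment at all. Apply the same rule to the two- and three-dimensional rates.

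Report an evaluable-only rate as a labelled sensitivity analysis. Define evaluable for that purpose, including how children entered without measurable or evaluable disease are treated.

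As clarification only, reword 9.1.2 and 9.1.4 so that the analysis takes place once each subject has been assessed at 6 months or has failed under 9.1.5, with no treated subject replaced. Reconcile the 24 in 3.1 with the 23 in section 9.1.

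The cost is a few changes of wording and somewhat lower reported response rates. No added visits, data or subjects are needed.
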